2.4. Statistical Analyses

The primary objective of this study is to determine the safety and tolerability of single subcutaneous doses of GSK2330811 in healthy Japanese participants. No formal hypotheses are being tested in this study and therefore no statistical analysis is planned.

2.5. Interim Analyses

An unplanned unblinded review of available exposure time-course data from the ongoing study cohort was initiated due to a safety related temporary study hold criterion being met. The unblinded data provided to CPMS and analysis report was documented in trial master file.

2.6. Final Analyses

The final planned primary analyses will be performed after the completion of the following sequential steps:

1. All participants have completed the study as defined in the protocol.
2. All required database cleaning activities have been completed and final database release (DBR) and database freeze (DBF) has been declared by Data Management.
3. All criteria for unblinding the randomization codes have been met.
4. Randomization codes have been distributed according to RandAll NG procedures.

3. ANALYSIS POPULATIONS

Population	Definition / Criteria	Analyses Evaluated
Screened	
 • All participants who signed the ICF and were screened for eligibility 	
 • Study Population • Screen Failures
Enrolled	
 • All participants who signed the ICF and were randomized into the study. 	
 • Study Population
Safety	
 • All randomized participants who received a full dose of study treatment. • Participants will be analysed according to the treatment they received. • Note: In the very unlikely case a participant is not randomized but receives at least one dose of study treatment, these participants will be listed separately. 	
 • Study Population • Safety • PK/PD selected tables and figures
Pharmacokinetic (PK)	
 • All participants in the Safety population who received at least one active dose of study treatment and had at least 1 non-missing PK assessment (Non-quantifiable values will be considered as non-missing values). • Participants will be analysed according to the study treatment they received. 	
 • PK • PK/PD selected figures

Refer to [Appendix 9](#): List of Data Displays which details the population used for each display.

CONFIDENTIAL

208564

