4.2. Number of Participants

Approximately ten participants will be enrolled and dosed (7 GSK2330811: 3 Placebo) with a view to ensuring 8 are evaluable (6 GSK2330811: 2 Placebo). See Section 9.2 for details. Evaluable is defined as a participant who has received a full dose and has attended all visits up to Day 56 and at least one of Day 84 or Day 126.

In rare instances, a participant may not be able to receive all 3 required injections and will receive a partial dose. In such circumstances, the participant will not be considered evaluable, but will be encouraged to remain in the study for the planned duration.

If any participant is non-evaluable for any reason, the participant may be replaced at the discretion of the sponsor in consultation with the investigator and assigned to the same treatment.

Up to a maximum of 14 participants may be enrolled and dosed.

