7. DISCONTINUATION OF STUDY INTERVENTION AND PARTICIPANT DISCONTINUATION/WITHDRAWAL

7.1. Discontinuation of Study Intervention

This is a single dose study. In rare instances a participant may not be able to receive all 3 injections and it may be necessary for the participant to permanently discontinue study intervention. If study intervention is discontinued, the participant will remain in the study for the planned duration.

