8.2.6. Hypersensitivity Reactions

As GSK2330811 is a humanized monoclonal antibody, it is considered unlikely that acute allergic reactions will occur in response to exposure; however, all participants should be monitored carefully for evidence of allergic response.

Participants should be instructed to report the development of rash, hives, pruritus, flushing, urticaria, vomiting, or other symptoms that may represent a hypersensitivity reaction to study intervention. It is important to recognize early signs of a hypersensitivity reaction and prevent progression to a severe reaction. In the case of a mild local reaction during dosing, study intervention administration may be reinitiated (with appropriate pre-medication if thought necessary) at the discretion of the investigator.

In the event of a suspected severe acute hypersensitivity reaction or anaphylaxis, sites should manage this in accordance with relevant local or national guidelines (for example, the Resuscitation Council (UK) Emergency Treatment of Anaphylactic Reactions Guidelines for Healthcare Providers (2008). In particular sites should:

- Discontinue administration of study intervention (if still ongoing), and not delay initial treatment due to an indefinite diagnosis.
- Ensure adrenaline, chlorphenamine, hydrocortisone, and a resuscitation trolley are immediately available.
- Assess the participant using the **A**irway, **B**reathing, **C**irculation, **D**isability, **E**xposure approach. In the event of a cardiac arrest, initiate cardiopulmonary resuscitation.
- Provide adrenaline according to relevant local/national guidelines if there is any compromise of the participant's airway, breathing or circulation:
- Provide high concentration oxygen via a non-rebreather mask; fluid resuscitation; initiate ECG monitoring and pulse oximetry; and monitor blood pressure.
- Administer an appropriate antihistamine (e.g., chlorphenamine maleate 10 mg by slow intravenous injection, or intramuscularly).
- Administer hydrocortisone 200 mg by slow intravenous injection, or intramuscularly.
- Acquire two blood samples for serum tryptase analysis:
 - As soon as possible after the onset of symptoms, and
 - Within 1-2 hours (but no later than 4 hours) from the onset of symptoms.

- Discuss the clinical situation with the relevant hospital medical and/or intensive care team and arrange transfer to hospital for further treatment and observation as indicated.

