9.3. Populations for Analyses

The following populations are defined:

Population	Description
Screened	All participants who signed the ICF and were screened for eligibility.
Enrolled	All participants who signed the ICF and are randomized into the study.
Safety	All randomized participants who received at least one dose of study treatment. Participants will be analysed according to the treatment they received. Note: In the very unlikely case a participant is not randomized but receives at least one dose of study treatment, these participants will be listed separately.
Pharmacokinetic	All participants in the Safety population who received at least one active dose of study treatment and had at least 1 non-missing PK assessment (Non-quantifiable values will be considered as non-missing values). Participants will be analysed according to the study treatment they received.

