2. SUMMARY OF KEY PROTOCOL INFORMATION

2.1. Changes to the Protocol Defined Statistical Analysis Plan

There was an unplanned interim analysis conducted due to safety related temporary study hold criterion being met and was not specified in the protocol.

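### The SAP restricts the Safety population to fully dosed participants, against the protocol and without declaring it, so a partly dosed participant drops out of every safety summary table

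*SAP*

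**What the plan says.** **Definitions.** Protocol 9.3 defines Safety as "All randomized participants who received at least one dose of study treatment", analysed by treatment received. SAP section 3 defines it as "All randomized participants who received a full dose of study treatment". The note in the same SAP cell, on non-randomised participants to be listed separately, keeps the looser condition: "In the very unlikely case a participant is not randomized but receives at least one dose of study treatment". The SAP's PK definition also keeps the protocol's wording (at least one active dose), but it is a subset of Safety.

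**Declared changes.** SAP 2.1 names one departure from the protocol: "There was an unplanned interim analysis conducted due to safety related temporary study hold criterion being met". It says nothing about populations.

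**Partial dosing.** Protocol 4.2 expects that in rare cases "a participant may not be able to receive all 3 required injections and will receive a partial dose". Such a participant is not evaluable but is asked to stay in follow-up, and "the participant may be replaced at the discretion of the sponsor in consultation with the investigator and assigned to the same treatment". Protocol 7.1 adds: "If study intervention is discontinued, the participant will remain in the study for the planned duration". Protocol 8.2.6 gives one possible cause: for a suspected severe acute hypersensitivity reaction, sites should "Discontinue administration of study intervention (if still ongoing), and not delay initial treatment due to an indefinite diagnosis". SAP 12.5.2 computes the active dose as injections times 150 mg, which allows for fewer than three.

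**Use of the population.** SAP section 7 bases the safety analyses on Safety. Appendix 9 assigns that population to Tables 3.1–3.23 and Figures 3.1–3.5. Listings 2–27 use Enrolled. Listings 28–33 (PK, OSM, TPO, EPO) use PK or Safety.

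**The concern.** Under the SAP rule, whether a participant counts in the primary analysis depends on something that happens after randomisation and may itself be the safety outcome. If a reaction to the first or second injection stops dosing, that participant and his event leave the tables that report the primary endpoints, which are numbers of participants. If dosing stops for an unrelated reason, such as a syringe malfunction, an event-free participant leaves the denominator and the reported rates can rise.

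In both cases the tables no longer describe the protocol's Safety population, and the SAP does not tell the reader so. A safety-related hold criterion was met in this study (SAP 2.1 and 2.5), so the safety tables are likely to be read closely.

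**Working it through.** **1. Are the two definitions really different?** Protocol 4.2 distinguishes a full dose from a partial one and uses full dose only to define an evaluable participant. Protocol 9.3 does not use that term for Safety. The SAP therefore carries part of the evaluability criterion into the Safety set. The note in the same cell and the PK definition still say at least one dose, so SAP section 3 is also inconsistent within itself.

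**2. Which displays are affected?** Counting populations in SAP Appendix 9:

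- Study population tables: 8 of 11 use Safety (all except 1.2, 1.5 and 1.7).
- Safety tables: 23 of 23 use Safety.
- PD tables: 6 of 6 use Safety.
- PK tables: 3 of 3 use PK, which is nested in Safety.
- Total tables: 8 + 23 + 6 + 3 = 40 of 43.
- Figures: 5 safety + 3 PK + 3 PD + 1 PK/PD = 12 of 12.

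These totals apply to a partly dosed active participant. A placebo participant is outside the PK population under either definition, so for him the reach is 8 + 23 + 6 = 37 tables and 5 + 3 = 8 figures.

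Table 3.7 covers adverse events leading to discontinuation of treatment or to withdrawal from the study. With a single dose, discontinuing treatment means not receiving all three injections. The discontinuation part of that table is therefore empty by construction under the SAP rule; the withdrawal part is not.

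For a partly dosed active participant, Listings 28–33 are closed as well, so his PK, OSM, TPO and EPO data appear in no planned display.

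**3. The plan's own figures.** Protocol Table 2 uses a Beta(1,1) prior. The posterior for x events in n is Beta(1 + x, 1 + n − x), and the limits are its 2.5% and 97.5% quantiles. This gives 0.32%–36.94% for 0/7, 3.19%–52.65% for 1/7, 0.36%–40.96% for 0/6 and 3.67%–57.87% for 1/6. All six rows of Table 2 reproduce, including the 2/7 and 2/6 rows.

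**4. Effect of one partly dosed active participant.** Planned active arm: 7.

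| Case | Protocol definition | SAP definition |
|---|---|---|
| His reaction is the only event, not replaced | 1/7 = 14.3% (3.2%–52.7%) | 0/6 = 0% (0.4%–41.0%) |
| Same, replaced on the same treatment | 1/8 = 12.5% | 0/7 = 0% (0.3%–36.9%) |
| He is event-free, one other participant has an event | 1/7 = 14.3% (3.2%–52.7%) | 1/6 = 16.7% (3.7%–57.9%) |
| No events in anyone | 0/7, upper limit 36.9% | 0/6, upper limit 41.0% |

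**5. A related contradiction.** SAP 12.3.1 classes an event starting exactly at the treatment start date/time as pre-treatment. SAP 12.6.2.1 moves certain partial adverse event start dates to the treatment start date and calls the result on-treatment, citing that same appendix. This affects the treatment-emergent flag. Tables 3.1–3.7 are not titled as treatment-emergent, so it is not shown to remove events from them.

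**The case against.** The best counter-argument is that the SAP only restates the protocol. One dose is three injections, so at least one dose could mean a complete dose. That reading is possible but weak: protocol 4.2 has separate terms for full and partial doses, and SAP section 3 uses both expressions in the same cell. What stands is that the protocol's wording could be clearer, so the corrected text should refer to injections.

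The second argument is that the exclusion would be visible. SAP 12.6.2 requires any participant left out of summaries to be documented with the reason in the study report. Table 1.5, on the Screened population, summarises the analysis populations. Listings 13–27 use Enrolled and cover adverse events, serious events, events leading to discontinuation, graded laboratory values, ECG, vital signs and immunogenicity. All of this is correct, and with about ten participants listings carry weight. It does not restore the tabulated counts, which are the primary endpoints, and it does not cover Listings 28–33.

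The third is that the effect may never arise. The protocol calls partial dosing rare and acute allergic reactions unlikely, and reports no hypersensitivity reactions in the first-in-human study. The three syringes are given close together. No hypothesis is tested. These points stand as limits on likelihood, but a population definition should give the right set if the foreseen case occurs.

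**Conclusion.** The SAP definition is wrong as written. It contradicts protocol 9.3, is not declared in SAP 2.1, and excludes from the primary safety summaries a participant whom the protocol expects and follows.

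The illustrated error is one participant among about seven on active drug, in either direction: 0% instead of 14.3%, or 16.7% instead of 14.3%. These cases assume one partly dosed active participant and, in the first, that he has the only event. The documents give no partial-dose rate and do not say whether one occurred. If none did, the two definitions give the same set. The individual safety data remain in the listings throughout. The treatment-emergent contradiction is real but secondary.

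**What to change.** 1. In SAP section 3, define Safety as all randomised participants who received at least one injection of study treatment, whether the dose was complete or partial, analysed by treatment received. The nested PK population then matches protocol 9.3 again without further edits.
2. If a restriction to fully dosed participants is intended, state and justify it in SAP 2.1.
3. Align SAP 12.3.1 with 12.6.2.1: pre-treatment is before the treatment start date/time and treatment-emergent is at or after it. Treat adverse events on the dosing date with no recorded time as treatment-emergent.

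The cost is SAP wording and a few programming conditions. No new data are needed.

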3.1. Protocol Deviations

Important protocol deviations (including deviations related to study inclusion/exclusion criteria, conduct of the trial, participant management or participant assessment) will be summarised and listed.

Protocol deviations will be tracked by the study team throughout the conduct of the study in accordance with the Protocol Deviation Management Plan **[Version 1, 25 Nov 2019]**.

- Data will be reviewed prior to unblinding and freezing the database to ensure all important deviations are captured and categorised on the protocol deviations dataset.
- This dataset will be the basis for the summaries and listings of protocol deviations.

A separate summary and listing of all inclusion/exclusion criteria deviations will also be provided. This summary will be based on data as recorded on the inclusion/exclusion page of the eCRF.

A separate table and listing of all COVID-19 related protocol deviations will be provided to capture the impact on visits and assessments.

CONFIDENTIAL

208564

4. CONSIDERATIONS FOR DATA ANALYSES AND DATA HANDLING CONVENTIONS

4.1. Study Treatment & Sub-group Display Descriptors

Treatment Group Descriptions			
RandAll NG		Data Displays for Reporting	
Code	Description	Description	Order in TFL ^[1]
A	GSK2330811 450 mg SC - PARALLEL	GSK2330811 450 mg	2
P	Placebo - PARALLEL	Placebo	1

NOTES:

1. Order represents treatments being presented in TFL, as appropriate.

4.2. Baseline Definitions

For all endpoints the baseline value will be the latest pre-dose assessment with a non-missing value, including those from unscheduled visits. If time is not collected, Day 1 (or Day -1 where applicable) assessments are assumed to be taken prior to first dose and used as baseline.

In case that triplicate assessments are performed, the mean of triplicate assessments at any given time point will be used as the value for that time point.

4.2.1. Derivations and Handling of Missing Baseline Data

If baseline data is missing, no derivation will be performed, and baseline will be set to missing. The baseline definition will be footnoted on all change from baseline displays.

Definition	Reporting Details
Change from Baseline	= Post-Dose Visit – Baseline
% Change from Baseline	= $100 \times [(Post-Dose Visit – Baseline) / Baseline]$
Nadir	= Lowest post-baseline value of endpoint for a participant ^[1]
Time (Days) to Nadir	= Study Day of Nadir – 1 ^[1]

NOTES:

- 1: When there are multiple instances of the lowest value then the nadir used for reporting will be the earliest occurrence of that value.
- Unless otherwise specified, the baseline definitions specified in Section 4.2. Baseline Definitions will be used for derivations for endpoints / parameters and indicated on summaries and listings.
- Unless otherwise stated, if baseline data is missing no derivation will be performed and will be set to missing.
- The baseline definition will be footnoted on all change from baseline displays. 'Note: Baseline is defined as the pre-dose Day 1 assessment, unless unavailable, in which case it is the latest pre-dose assessment.'
- If there are multiple measurements (i.e. ECG) the derivation will be based on the average values where available.

CONFIDENTIAL

208564

4.3. Examination of Covariates, Other Strata and Subgroups

There is no planned examination of covariates, other strata and subgroup analyses due to the small overall sample size.

4.4. Multiple Comparisons and Multiplicity

There is no adjustment for multiplicity in this phase 1 study.

4.5. Other Considerations for Data Analyses and Data Handling Conventions

Other considerations for data analyses and data handling conventions are outlined in the appendices:

Section	Component
12.2	Appendix 2 : Assessment Windows
12.3	Appendix 3 : Study Phases and Treatment Emergent Adverse Events
12.4	Appendix 4 : Data Display Standards & Handling Conventions
12.5	Appendix 5 : Derived and Transformed Data
12.6	Appendix 6 : Reporting Standards for Missing Data
12.7	Appendix 7 : Values of Potential Clinical Importance

CONFIDENTIAL

208564

5. STUDY POPULATION ANALYSES

5.1. Overview of Planned Study Population Analyses

The study population analyses will be based on the ‘Safety’ population, unless otherwise specified.

Study population analyses including analyses of subject’s disposition, protocol deviations, demographic and baseline characteristics, concomitant medications, and exposure and treatment compliance will be based on GSK Core Data Standards. Details of the planned displays are presented in [Appendix 9: List of Data Displays](#).

6. EFFICACY ANALYSES

There are no efficacy analyses included in this study.

7. SAFETY ANALYSES

The safety analyses will be based on the “Safety” population, unless otherwise specified.

7.1. Adverse Events Analyses

Adverse events analyses including the analysis of adverse events (AEs) and Serious (SAEs) will be based on GSK Core Data Standards. The details of the planned displays are provided in [Appendix 9: List of Data Displays](#).

7.2. Clinical Laboratory Analyses

Laboratory evaluations including the analyses of chemistry laboratory tests, haematology laboratory tests, urinalysis, and liver function tests will be based on GSK Core Data Standards. The details of the planned displays are in [Appendix 9: List of Data Displays](#).

Descriptive statistics (n, arithmetic mean, standard deviation, median, minimum, and maximum) will be calculated for nadirs for platelet count and haemoglobin.

Descriptive statistics (n, median, minimum, maximum and range) will also be calculated for time to nadir for platelet count and haemoglobin.

Laboratory safety will be graded using CTCAE criteria version 5. CTCAE grade 1 or higher safety laboratory results will be presented (where CTCAE grading applies).

7.3. Other Safety Analyses

The analyses of non-laboratory safety test results including ECGs and vital signs will be based on GSK Core Data Standards, unless otherwise specified.

A separate listing to capture the COVID-19 infection assessment of participants based on new eCRF page will be provided.

The details of the planned displays are presented in [Appendix 9: List of Data Displays](#).

CONFIDENTIAL

208564

8. IMMUNOGENICITY ANALYSES

The immunogenicity analyses will be based on the “Safety” population, unless otherwise specified. The immunogenicity analysis summarises the incidence of confirmed anti-drug antibodies and lists the titre of immunogenicity results.

Details of the planned displays are presented in [Appendix 9: List of Data Displays](#).

9. PHARMACOKINETIC ANALYSES

9.1. Secondary Pharmacokinetic Analyses

9.1.1. Endpoint / Variables

9.1.1.1. Drug Concentration Measures

Refer to [Appendix 4](#): Data Display Standards & Handling Conventions (Section 12.4.3 Reporting Standards for Pharmacokinetic).

9.1.1.2. Derived Pharmacokinetic Parameters

Pharmacokinetic parameters will be calculated by standard non-compartmental analysis according to current working practices and using the currently supported version of WinNonlin. All calculations of non-compartmental parameters will be based on actual sampling times. Pharmacokinetic parameters listed will be determined from the plasma concentration-time data, as data permits.

Parameter	Parameter Description
Cmax	
 Maximum observed concentration. 
Determined directly from the concentration-time data.

Tmax	
 Time to reach Cmax. 
Determined directly from the concentration-time data.

AUC(0-t)	
 Area under the concentration-time curve from time zero to the time of last quantifiable concentration (C(t)). Calculated using the linear trapezoidal rule for each incremental trapezoid and the log trapezoidal rule for each decremental trapezoid.
AUC(0-inf)	
 Area under the concentration-time curve from time zero to infinity Calculated as $AUC(0-\infty)=AUC(0-t)+C(t)/\lambda_z$. AUC(0-inf) should not be reported if the area coming from extrapolation is greater than 20% of AUC(0-inf).
%AUCex	
 The percentage of AUC (0-inf) obtained by extrapolation will be calculated as: $[AUC(0-\infty) - AUC(0-t)] / AUC(0-\infty) \times 100$
t1/2	
 Terminal half-life Calculated as $t_{1/2}=\ln 2/\lambda_z$.
CL/F	
 Apparent systemic clearance
Vss/F	
 Apparent volume of distribution at steady state
tlast	
 Time of last quantifiable concentration

NOTES:

- Additional parameters may be included as required.
- λ_z is the first order rate constant associated with the terminal (log-linear) portion of the curve. Estimated by linear regression of time vs. log concentration

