4. STUDY DESIGN

4.1. Overall Design

This is a randomised, double-blind (sponsor-open), placebo-controlled, single-centre study with single SC doses of GSK2330811 administered to healthy male Japanese participants.

- Participants will attend a screening visit at the clinical unit within 30 days of Study Day 1. If eligible for the study, participants will return on Day -1 for overnight admission to the unit.
- Participants will be randomized to either GSK2330811 or placebo in an approximate ratio of 7:3.
- Approximately 10 eligible participants will be admitted to the clinical unit on the day prior to dosing (Day-1). On Day 1, each participant will receive a single SC dose of GSK2330811 or placebo, administered as three separate SC injections. Participants will then remain as an in-patient until discharged on Day 2 after assessments have been performed.
- Participants will then return to the clinical unit for outpatient visits as described in the SoA.
- The final follow up visit will be at the clinical unit on Day 126.
- The maximum dose will not exceed 450 mg SC.

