4.4. Scientific Rationale for Study Design

The proposed 450 mg single SC dose in Japanese participants is anticipated to result in exposure comparable to the 6 mg/kg (average 417 mg, range 375-443 mg) single SC dose tested in Caucasian participants in the FTIH study 201246 allowing a comparative assessment of ethnic sensitivity in terms of safety, tolerability and PK and PD in a Japanese population. Furthermore, a dose of 450 mg SC aligns with the highest anticipated dose to be administered in the global clinical studies with GSK2330811.

In addition, this study will be conducted in healthy male participants for the following reasons:

- Patients with inflammatory and fibrotic diseases may have existing comorbidities or be taking concomitant medications that may confound the analysis.
- It is anticipated that patients would derive little or no benefit from a single dose of GSK2330811, but that taking part in the study might interfere with their ability to receive other potentially efficacious therapies.
- Animal reproductive toxicity studies have not yet been carried out with GSK2330811 and therefore the benefit-risk of enrolling women of child-bearing

potential in this study, where they are unlikely to derive any direct benefit from a single dose of GSK2330811, does not support their inclusion. Moreover, enrolling only male participants will facilitate comparison with data from study 201246, a single-dose FTIH study of GSK2330811 in predominantly male Caucasian participants [Reid, 2018].

This study will include a placebo arm to ensure that the treatment-attribution of adverse events (AEs) is appropriately blinded and to provide control data for the PD and safety laboratory assessments.

The duration of follow-up will be about 126 days, which will be approximately 5 half-lives of GSK2330811 (half-life of between 19 to 25 days) [GlaxoSmithKline Document Number 2016N284919_02, 2019].

Exploratory endpoints have been chosen to confirm target engagement and further investigate PK/PD relationships in the blood.

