6.1. Study Intervention(s) Administered

This study will use a pre-filled syringe (PFS): Becton Dickinson's UltraSafe Plus Safety Syringe Device. Instructions for use of the PFS medical device are provided in the Study Reference Manual (SRM).

Intervention Name	GSK2330811	Placebo
Type	Drug	Placebo
Dose Formulation	50mM Sodium Acetate Trihydrate, 51mM Sodium Chloride, 1% (w/v) L-Arginine, 0.05mM Edetate Disodium Dihydrate (EDTA) and 0.02% Polysorbate 80 in Water for Injection USP, pH 5.5	Normal saline (0.9% sodium chloride)
Unit Dose Strength(s)	150mg/ml	N/A
Dosing Instructions	Administered by study personnel. 3 injections to be used to provide 450mg SC dose.	Administered by study personnel. 3 injections will be used to match active doses administered.
Route of Administration	SC injection to abdomen	SC injection to abdomen
IMP and Non-investigational medicinal product (NIMP)	IMP	NIMP

Intervention Name	GSK2330811	Placebo
Sourcing	Provided by the Sponsor	Provided by the Sponsor
Packaging and Labelling	Study intervention will be provided in a pre-filled safety syringe. Label content will be in accordance with the country's regulatory requirements	Study intervention will be provided in a pre-filled safety syringe. Label content will be in accordance with the country's regulatory requirements
[Current/Former Name(s) or Alias(es)]	Anti-OSM	N/A

GSK2330811 is a humanised monoclonal antibody and all formulation ingredients have been previously used in the clinic.

SC GSK2330811 is administered as multiples of 150 mg injections, each provided as a pre-filled safety syringe.

In an individual participant, injections should be administered into the abdomen and should be separated by a minimum of 2 cm. The location of the injections (abdominal quadrant) will be recorded.

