9.4.3. Secondary Endpoint(s)

9.4.3.1. Pharmacokinetic parameters

The pharmacokinetic (PK) analyses will be based on the “Pharmacokinetic” population. Individual plasma concentration-time data will be graphically displayed and summary statistics will be produced by time point. Plasma GSK2330811 concentration-time data will be analysed by non-compartmental methods. Calculations will be based on the actual sampling times recorded during the study. From the plasma concentration-time data, the following pharmacokinetic parameters will be determined, as data permit: maximum observed plasma concentration (C_{max}), time to C_{max} (T_{max}), area under the plasma concentration-time curve (AUC_[0-t], AUC_[0-inf]), terminal half-life (t_{1/2}), apparent volume of distribution at steady state (V_{ss}/F) and apparent systemic clearance (CL/F).

Descriptive statistics (n, arithmetic mean, standard deviation, 95% CI, minimum, median and maximum,) will be calculated for all pharmacokinetic parameters. In addition, for

log_e-transformed variables geometric mean, 95% confidence interval, standard deviation on the log scale and %CVb will be provided.

Full details of planned secondary analysis will be specified in the RAP.

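### Vss/F from non-compartmental analysis of a single SC dose includes absorption time: state its formula and bias, and report Vz/F alongside it under its own label

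*SAP*

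**What the plan says.** Vss/F is one of the secondary PK endpoints in Protocol section 3 and SAP 2.2. Protocol 9.4.3.1 lists the "apparent volume of distribution at steady state" among parameters to be obtained from plasma data by non-compartmental methods. SAP 9.1.1.2 repeats this: "Pharmacokinetic parameters will be calculated by standard non-compartmental analysis", in WinNonlin, following current working practices.

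The SAP gives formulas for AUC(0-inf), %AUCex and t1/2. For Vss/F it gives only the description "Apparent volume of distribution at steady state". Neither document mentions mean residence time, AUMC or mean absorption time.

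Dosing is extravascular only. Protocol 4.1 states that "each participant will receive a single SC dose of GSK2330811 or placebo, administered as three separate SC injections", and the route in Protocol 6.1 is "SC injection to abdomen". There is no IV arm, and no IV reference data are cited.

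Vz/F is not listed, although its ingredients are. CL/F and AUC(0-inf) are planned, and lambda_z "is the first order rate constant associated with the terminal (log-linear) portion of the curve". The notes to the same table add: "Additional parameters may be included as required". SAP 9.1.2 plans descriptive statistics for Vss/F, plus geometric mean, 95% CI and %CVb on the log scale.

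**The concern.** The usual non-compartmental steady-state volume is clearance times mean residence time. After an SC dose, the residence time read from the plasma curve is the disposition residence time plus the mean absorption time. Without IV data the two parts cannot be separated non-compartmentally. The product is then a volume plus a term that depends on how fast the drug leaves the injection site.

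The bias is upward for any absorption time above zero, and it does not shrink with more participants. The parameter would be reported under a label that does not describe it. Two populations with the same volume and clearance but different absorption would show different values of Vss/F, and a reader could take that for a difference in volume.

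**Working it through.** The documents give no value or formula for Vss/F, so there is no stated figure to reproduce.

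**Identities** (MAT = mean absorption time)
- MRT(SC) = AUMC/AUC = MRT(IV) + MAT
- CL/F × MRT(SC) = true Vss/F + CL/F × MAT
- One compartment, first-order absorption: MRT(IV) = 1/k and MAT = 1/ka, so the relative excess is k/ka.
- Vz/F = (CL/F)/lambda_z = Dose/(lambda_z × AUC(0-inf)), with no absorption term.

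**Inputs**
- Terminal half-life: "half-life of between 19 to 25 days" (Protocol 4.4).
- AUC(0-inf) at 6 mg/kg: 27681 h·µg/mL (Protocol 9.2, Table 3).
- Average dose at 6 mg/kg: 6 × 69.5 = 417 mg (Protocol 9.2).
- Absorption rate constant ka: assumed 0.15 to 0.6 per day, i.e. MAT 6.7 to 1.7 days. The documents do not give it.

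**Relative excess, one compartment**
- k = ln2/19 = 0.0365 per day; k = ln2/25 = 0.0277 per day.
- Largest: 0.0365/0.15 = 24.3%. Smallest: 0.0277/0.6 = 4.6%.
- Taking MAT directly as 2 to 7 days gives 2 × 0.0277 = 5.5% up to 7 × 0.0365 = 25.5%.

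**Excess in litres**
- CL/F = 417,000 µg / 27681 h·µg/mL = 15.1 mL/h = 0.36 L/day.
- CL/F × MAT = 0.7 L (2 days), 1.4 L (4 days), 2.5 L (7 days).
- Vz/F = 9.9 L (half-life 19 days), 11.5 L (22 days), 13.0 L (25 days).

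**Check on the trial's sampling days.** Error-free profiles for 450 mg were analysed non-compartmentally (linear-up, log-down) at MAT 2, 4 and 7 days. CL/F was 0.36 L/day throughout. The two-compartment cases are assumed, each with true Vss/F = 10 L.

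| Disposition | True Vss/F (L) | Uncorrected Vss/F, excess at MAT 2 / 4 / 7 d | Vz/F against true Vss/F |
|---|---|---|---|
| One compartment, 22 d | 11.5 | +6.9 / +13.4 / +23.1% | +0.3 to +0.9% |
| Central 7 L, peripheral 3 L, Q 1.0 L/d | 10 | +7.9 / +15.2 / +26.4% | +3.8 to +4.3% |
| Central 6 L, peripheral 4 L, Q 0.8 L/d | 10 | +7.8 / +15.1 / +26.2% | +8.3 to +8.7% |
| Central 5 L, peripheral 5 L, Q 0.5 L/d | 10 | +7.8 / +15.0 / +26.0% | +21.1 to +21.4% |

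Subtracting the known MAT brings Vss/F back to within about 1% of truth in every case, which confirms the source of the excess. Vz/F barely moves with MAT, but in the two-compartment cases it lies 4% to 21% above true Vss/F.

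**What this does to a comparison.** In the one-compartment case, uncorrected Vss/F is 12.27 L at MAT 2 days and 13.01 L at MAT 4 days. The ratio is 13.01/12.27 = 1.06: an apparent 6% difference in volume where there is none.

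**The case against.** **The formula is not seen.** The SAP defers to working practices that are not in the documents. Uncorrected CL/F × MRT is the usual calculation, not one the documents state. This stands as a condition on the point, and it is also a reason to write the formula down.

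**Vz/F is not Vss/F.** A reader might infer that Vz/F should simply replace Vss/F as the better estimate of the same thing. The documents do not support that. The sponsor describes this drug with an mPBPK model (Protocol 4.5 and 9.2), not as a single compartment. In the last case in the table, at MAT 2 days, Vz/F is further from true Vss/F (+21%) than the uncorrected Vss/F is (+8%). Replacement would also remove a secondary endpoint named in the protocol, in a SAP that already reports an unplanned unblinded review of exposure data (SAP 2.5). This objection stands in full.

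**Little rests on Vss/F.** A reader might also infer that the bias undermines the ethnic comparison or later dose selection. No section uses Vss/F for either. Table 1 compares Cmax and AUC, the sample-size simulations use AUC(0-inf), and Protocol 4.4 speaks of PK in general. No Vss/F value from study 201246 is given. If that study derived it the same way and absorption was similar, the bias would largely cancel, but the documents establish neither. No hypothesis is tested.

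**Precision is limited anyway.** The 95% CI for AUC(0-inf) from six participants in study 201246, 21748 to 35233 around 27681, runs from about −21% to +27%. Much of the 5% to 24% range is modest beside that. It is still systematic and does not average out.

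**Conclusion.** The point holds in a limited form. Computed as CL/F × MRT without an absorption correction, Vss/F is overstated by CL/F × MAT. The direction is certain for any absorption time above zero. The size is about 5% to 24% in a one-compartment case; it rests on the protocol half-life and on an assumed ka of 0.15 to 0.6 per day, and scales directly with that assumption.

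Vz/F avoids the absorption term, provided the terminal slope reflects elimination, but it is a different quantity and must be read as such. The impact is modest: one descriptive secondary parameter is affected, while Cmax, AUC, CL/F, t1/2 and the sample size are not.

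**What to change.** 1. In SAP 9.1.1.2, add Vz/F = (CL/F)/lambda_z and carry it into SAP 9.1.2 and Tables 4.2 and 4.3. Label it Vz/F, as the volume free of absorption time, and note that it can exceed Vss when disposition is multi-compartment.
2. Keep Vss/F, since the protocol names it, and state its formula in SAP 9.1.1.2. If that is CL/F × MRT, footnote Tables 4.2 and 4.3 to say that MRT includes absorption time and the value is therefore biased upward.
3. State that Vss/F will not be interpreted as a pure volume when populations are compared.
4. Record the addition and the clarification in SAP 2.1.

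The cost is one extra parameter and a footnote. Vz/F needs no new samples or data, and the SAP already allows further parameters. No protocol endpoint is removed.
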